1.0 SPECIFIC STUDY AIMS

Painful peripheral neuropathy (PPN) is a common sequela of chemotherapy that severely impacts the quality of life in cancer patients (1). There is no biomarker, tool, or method to predict the development or progression of painful chemotherapy-induced peripheral neuropathy (CIPN). The pathophysiology of CIPN remains insufficiently understood; current treatment and prevention strategies provide only modest benefit to patients (2). In this study, we will test the utility of the Diode Laser fiber type Selective Stimulator (DLss) (3) in identifying patients at risk of developing PPN.

Small-diameter lightly myelinated A δ and unmyelinated C cutaneous nociceptive fibers transmit pain from the peripheral to central nerve system. A δ and C fibers are divided by sensitivity: heat, mechanical (tactile), and chemical stimulation, and epidermal versus dermal location. In animals and humans, dying back intra-epidermal fibers lead to reduced pain sensitivity, rather than pain, which suggests fiber loss alone is not sufficient to explain the development of neuropathic pain (4-9). In contrast, abnormally high spontaneous activity of nociceptive fibers, specifically dermal C mechano-insensitive (CMi) fibers, is associated with peripheral ongoing neuropathic pain (10-12)(13-15). Therefore, a tool that can measure, track, and predict the development of abnormal function of A δ and C fibers is a critical unmet medical need.

Most diagnostic tests to study nociceptive fibers are able to measure the loss of pain sensitivity in epidermal fibers (4-9). However, these tests are not fiber-type selective (11). Only microneurographic recording is able to separate fiber type and to access single fibers (16). Though due to complexity, microneurography is unpractical in the clinic. In contrast, we developed and patented DLss, which can be used at the bedside to safely and selectively stimulate A δ and C fibers in superficial and deep skin(14-23). Our preliminary DLss data demonstrates that patients with painful CIPN, who have decreased epidermal A δ and C-fiber densities, have increased A δ pain thresholds, while C-fiber thresholds are intact (20). The A δ :C pain threshold ratio was consistently higher in CIPN than healthy volunteers.

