Based on these preliminary data, *we propose that the A δ :C pain threshold ratio, as measured by the DLss during chemotherapy, will identify those patients at risk of developing pain during their treatment.* Ultimately, this will help us identify patients who 1) may benefit from a change in their treatment to prevent CIPN and 2) patients who would be the best candidates for interventional trials testing new drugs for the prevention of PPN.

Aim 1: Demonstrate that the A δ :C pain threshold ratio is significantly higher in patients with painful CIPN than in patients with painless CIPN.

Ovarian cancer annually affects about 20,000 women in the US and causes 14,000 deaths (1999–2012 Cancer Incidence and Mortality Data, <http://www.cdc.gov/cancer/ovarian/statistics/>) (24) Ovarian cancer patients' first line chemotherapy regimen is typically a taxane combined with platinum. These drugs are known to cause CIPN neuropathic symptoms in up to 70% of patients; a large portion of those patients develop painful CIPN (25, 26). The combination of taxane with platinum may increase development of CIPN in 1.5 times compared to just taxane application(25). As a result, ovarian cancer patients have a high overall burden of painful CIPN. Though the exact mechanism of nerve damage may differ between taxanes and platinum drugs, they both result in painful CIPN. Here we will examine the underlying shared pathophysiology

of neuropathic pain. We will evaluate the DLss in [64] ovarian cancer patients with painful and painless neuropathy during initial taxane combined with platinum treatment, to determine their A δ :C pain threshold ratios. Presence or absence of pain will be determined via pain questionnaire and numeric pain scale (27). Enrolling 25 patients with painful CIPN and 25 patients with painless CIPN, we will have 80% power to detect a 1.31 fold A δ :C pain threshold ratio.

Aim 2: Determine the A δ :C ratio over time in patients with CIPN.

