4.4 Description of Study Activities

Screening within 14 days prior to the first DLss testing:

- Written informed consent must be obtained from the subject prior to performance of any study-specific tests or evaluations. Subjects must be consented to undergo the pain questionnaires and DLss testing. If patient remains in active screening, consent does not need to be repeated if more than 14 days from DLss testing.

- Subjects will be asked to call and reschedule testing appointments if they have pain ≥ 50 on a scale of 0-100 (0=no pain, 100= worst pain imaginable) on the day of the scheduled test
- Eligibility criteria
- Headache assessment: assess for chronic daily headache or headache more than 14 days of the last month
- Demographics: birth date, race/ethnicity, and gender at birth.
- Medical history
- Cancer history including prior chemotherapy for malignancy
- Prior and concomitant therapy (including all previous therapy for malignancy, radiation, surgery, concomitant medications including OTC drugs, herbs, and St. John's Wort) taken in the week prior to DLss testing.

Study Visit 1 (9 weeks +/- 1 week from cycle 1, day 1 of chemotherapy)

- Concomitant medications taken in the last week
- Cumulative dose of each chemotherapy (As calculate by dose in mg x number of doses)
- Headache assessment as above
- Pain Questionnaires:
 - o Numeric Pain Scale: Patients will be asked to rate their overall pain on a scale from 0 to 100, where 0 is no pain and 100 is the worst imaginable pain (27, 46). Patients who are experiencing pain ≥ 50 despite intervention will be asked to reschedule testing. If needed, the patient will be referred to their MD for standard of care pain control measures. Painful neuropathy will be defined as pain scale ≥ 10 .
 - o Neuropathic Pain Questionnaire (NPQ):

This test will take less than 6 minutes to complete.

The NPQ was initially validated in 528 chronic pain patients from several clinics. This test is able to differentiate neuropathic pain patients from non-neuropathic pain patients. The NPQ may be used for the initial screening of neuropathic pain patients. It also has the ability to provide a quantitative measure for the descriptors important in the diagnosis and assessment of neuropathic pain. Consequently, it can be used for monitoring of neuropathic pain treatments and as an outcome measure.

For additional details: <https://www.ncbi.nlm.nih.gov/pubmed/12966256>.
A copy is included as **Appendix C**.

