5.0 STATISTICAL CONSIDERATIONS

5.1 Outcome Measurements

5.1.1 Outcome Measure for Aim 1

The primary outcome measure of this study is the difference in the “A δ :C pain threshold ratio” for patients with a painless response to chemotherapy versus painful neuropathy, as measured using the DLss.

The “A δ :C pain threshold ratio” is calculated using the A δ -fiber and C-fiber pain thresholds determined using the protocol outlined in **section 4.4**.

Each patient will have 2 testing sessions:

- 1) 9 weeks +/- 1 week from cycle 1, day 1 of chemotherapy
- 2) 21 weeks +/- 2 weeks after first dose of chemotherapy for ovarian cancer

This is not a safety outcome.

5.1.2 Outcome Measure for Aim 2

The second outcome measure of this study is the correlation between the “A δ :C pain threshold ratio” and the development of pain.

We will generate a Spearman correlation coefficient for the “A δ :C pain threshold ratio” obtained at the first testing session and the presence or absence of pain at the time of the second test.

This is not a safety outcome.

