5.2 Analysis plan

The A δ :C pain threshold ratio will be recorded for each eligible and evaluable patient for both time points. We will calculate the average value of this parameter for each group (A and B) on a logarithmic scale. Then we will use a standard statistical two side t-test to compare the “A δ :C pain threshold ratio” in the painless CIPN group to the painful CIPN group. We hypothesize that the painful CIPN group will have statistically significantly higher value “A δ :C pain threshold ratio” than those without.

To assess whether the “A δ :C pain threshold ratio” predicts future painful or painless CIPN, we will conduct logistic regression analysis of the binary pain value (pain or no pain) at the time of the second testing (independent variable) on the “A δ :C pain threshold ratio” at the time of the first testing (dependent variable). It will allow us to estimate whether the “A δ :C pain threshold ratio” predicts the chances of a patient to develop pain.

As an exploratory analysis, we will explore if the “A δ :C pain threshold ratio” obtained at

the first testing session predicts an increase in the numeric pain scale at the second testing session.

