5.3 Sample size

The power analysis of the preliminary data presented here was conducted by [name] (Stanford). The analysis was done on the natural logarithm scale and converted back using anti-logarithms. The geometric mean (GM) ratio of chemotherapy was 1.58 times the GM for healthy group. The GM in the diabetic group was 1.38 times the GM of the healthy group. The most variable group (Diabetics) had a standard deviation (log scale) of 0.33 and this value was used for sample size calculations.

These calculations showed that sample size of 25 subjects in each group will have 80% power to detect a 1.31 fold A δ :C pain threshold ratio in patients with painful versus painless CIPN. Based on the analysis of our preliminary data, we expect the effect size to be larger than 1.31.

It is possible that we will have more patients accrued to Group B compared to Group A because uncomfortable patients may not want to participate in as great a number. In this case, we will consider use using an “unbalanced” (“non-symmetrical”) statistical design, i.e. a design with unequal number of subjects in the two groups. If we get fewer than 25 patients with pain we will increase the number of patients in the group without pain to preserve the power of 80% in order to detect the effect size. If this approach is necessary, we will apply for a no-cost extension of the NIH SBIR.

Table 5.1 shows several possible combinations of sample sizes which will assure the power 80% to detect the effect size 1.31. The sample sizes were calculated using SAS 9.14 software, procedure proc power. The calculations are based on the use of a t-test on the natural logarithm scale with a standard deviation of 0.33, detectable effect size 0.24 on the log scale.

| Scenario | Subjects with pain | Subjects without pain |
|----------|--------------------|-----------------------|
| 1 | 25 | 25 |
| 2 | 24 | 26 |
| 3 | 23 | 27 |
| 4 | 22 | 28 |
| 5 | 21 | 29 |
| 6 | 20 | 31 |
| 7 | 19 | 34 |
| 8 | 18 | 37 |
| 9 | 17 | 42 |

Based on the new patient volume in the women’s cancer center, we expect to recruit 50 patients in 12 months. However, should the study require a non-symmetric statistical

method and its clear we will not be able to recruit 59 patients (scenario 9), we will we will request a12 month no-cost extension from the NIH/NCI.

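### The Aim 2 outcome measure (5.1.2) is a Spearman coefficient against yes/no pain: section 5.2 never uses it and its size does not measure discrimination, so the AUC should be named instead

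*Combined protocol and SAP*

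**What the plan says.** Section 1.0 gives the purpose as prediction for individual patients: "we will test the utility of the Diode Laser fiber type Selective Stimulator (DLss) (3) in identifying patients at risk of developing PPN". It proposes that the ratio measured during chemotherapy "will identify those patients at risk of developing pain during their treatment".

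For Aim 2, section 5.1.2 states: "We will generate a Spearman correlation coefficient for the" Aδ:C ratio "obtained at the first testing session and the presence or absence of pain at the time of the second test". It gives no target value and no confidence interval. The second variable is binary; section 4.4 sets the cut: "Painful neuropathy will be defined as pain scale ≥ 10".

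Section 5.2 does not mention the Spearman coefficient. For prediction it says "we will conduct logistic regression analysis of the binary pain value (pain or no pain) at the time of the second testing (independent variable", and it labels the Visit 1 ratio the dependent variable, so the two roles are reversed as written. For Aim 1 it plans a two-sided t-test on the log ratio. An exploratory analysis asks whether the Visit 1 ratio predicts a rise in the numeric pain scale. No section plans an AUC, sensitivity, specificity or cut-off.

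**The concern.** There are two problems. First, the named outcome measure and the planned analysis are different statistics, so it is unclear which one is the Aim 2 result.

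Second, a Spearman coefficient is normally judged against a maximum of 1. With a binary second variable it cannot get there, and its value depends on the share of patients with pain as well as on how well the ratio separates them. A modest coefficient could reflect weak separation, an uneven split, or both. The study is meant to show whether a bedside test can pick out patients at risk and to support a larger validation study. For that the natural summary is the probability that a patient with later pain has the higher ratio (the AUC), with its precision. The plan does not report it.

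**Working it through.** **Inputs**
- Aim 1 planning values (5.3): 25 per group, 80% power, 1.31-fold, log-scale SD 0.33. Two-sided test (5.2). Alpha is not stated; 0.05 is assumed.
- Most unbalanced split allowed (Table 5.1, scenario 9): 17 with pain, 42 without, a share of 17/59 = 0.288. This is a Visit 1 split.
- Completers (3.3): 20% dropout from 50, about 40 patients.
- Visit 2 pain share p: not given. The values below are assumed.

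**Step 1: the plan's own figure.** With ln(1.31) = 0.270 and SD 0.33, the standardized difference is 0.270/0.33 = 0.818. The t-test power at 25 per group is 80.9%, so the statement "sample size of 25 subjects in each group will have 80% power to detect a 1.31 fold" ratio is reproduced. Section 5.3 also prints the log-scale effect as 0.24, which does not equal ln(1.31) and would give 71.2% power; I use 0.270, which is what Table 5.1 reproduces with. The documents give no power or target for Aim 2.

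**Step 2: the identity.** For an untied continuous score and a binary variable with share p,

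rho = (2·AUC − 1) · sqrt(3p(1−p)) · n/sqrt(n² − 1).

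The last factor is 1.0003 at n = 40 and can be ignored. Simulation with 200,000 patients per scenario agreed with the identity.

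**Step 3: the ceiling (AUC = 1)**
- p = 0.50: sqrt(3 × 0.50 × 0.50) = 0.866
- p = 0.288: sqrt(3 × 0.288 × 0.712) = 0.784
- p = 0.20: sqrt(3 × 0.20 × 0.80) = 0.693

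Direct calculation on perfectly separated data gave 0.866 (20:20), 0.785 (17:42) and 0.693 (8:32). Ties from the 100 mA steps barely matter: at 20:20 the ceiling is 0.87 with 10 distinct levels and 0.89 with 4.

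**Step 4: the same discrimination at different shares.** Assume that the 1.31-fold difference and SD 0.33 also hold for the Visit 1 ratio between patients with and without Visit 2 pain, and that the ratio is lognormal. Then AUC = Φ(0.818/√2) = 0.719 and 2·AUC − 1 = 0.437.

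| Pain share p | Ceiling | rho at AUC 0.719 |
|---|---|---|
| 0.50 | 0.87 | 0.38 |
| 0.288 | 0.78 | 0.34 |
| 0.20 | 0.69 | 0.30 |
| 0.10 | 0.52 | 0.23 |

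Read the other way, rho = 0.35 means AUC 0.70 at p = 0.5, 0.72 at 0.3, 0.75 at 0.2 and 0.84 at 0.1.

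**Step 5: precision of the AUC.** The Hanley-McNeil standard error at AUC 0.719 with 20 per outcome class is 0.081, so the 95% CI is 0.719 ± 1.96 × 0.081, about 0.56 to 0.88. With 40 completers split 12:28 it is 0.53 to 0.90, and split 8:32 it is 0.50 to 0.94.

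**The case against.** A reader might infer that the Spearman analysis is invalid. It is not. Against a binary variable it is equivalent to a rank-sum test, and its test of no association stands. Section 5.1.2 calls it a correlation and does not present it as accuracy.

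A reader might also infer that the coefficient swings widely or cannot be compared with another sample. The documents do not support that. From p = 0.50 to 0.288 it moves by about 0.04. The standard error of rho at 20:20 is about 2 × 0.081 × 0.866 = 0.14, so the shift is roughly a quarter of one standard error. It grows only if Visit 2 pain is uncommon. If the pain counts are reported, the AUC can be recovered as 0.5 + rho/(2·sqrt(3p(1−p))). The enrollment quota fixes the Visit 1 split, not the Visit 2 share.

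The logistic regression in 5.2 covers prediction in part. Run with pain as the response, its odds ratio is not tied to the pain share. It is not the outcome named in 5.1.2, however, and no discrimination measure is planned from it.

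A further tempting step is to fault the Aim 1 t-test, because at 25 per group a difference of 2.011 × 0.33 × sqrt(2/25) = 0.188, or 1.21-fold, is already significant and implies an AUC of only 0.66. But Aim 1 asks whether group values differ, the t-test answers that, and 5.3 expects an effect above 1.31-fold.

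Finally, the AUC is not free of case mix. Group A patients already have pain at Visit 1, so an AUC over all completers mixes persistence with new onset. This objection stands, and the fix addresses it.

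**Conclusion.** The point holds as a cheap improvement, not as an invalidating error. Sections 5.1.2 and 5.2 name different statistics for Aim 2. The coefficient in 5.1.2 has a ceiling of 0.87 or less and reads 0.38, 0.34 or 0.30 for the same AUC of 0.72 at pain shares of 50%, 29% and 20%. What is missing is a reported measure of discrimination with its uncertainty, which the stated purpose calls for.

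The ceiling follows from the binary variable and an essentially continuous ratio. The rho and AUC values rest on two assumptions: the Visit 2 shares, and the carry-over of cross-sectional planning values to later pain. Between shares of 0.3 and 0.7 the effect on rho is modest (0.35 to 0.38).

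**What to change.** - In 5.1.2, make the Aim 2 outcome measure the AUC (c-statistic) of the Visit 1 log ratio for Visit 2 pain, with a 95% CI and a named interval method. Fix the direction in advance (higher ratio, more pain) so that a value below 0.5 stays visible.
- In 5.2, state Visit 2 pain as the response and the Visit 1 log ratio as the predictor, and take the AUC from that model so that the two sections agree.
- Report the number with and without pain at Visit 2. Also give, as a descriptive result, the AUC among patients without pain at Visit 1.
- Leave the Aim 1 t-test as it is. A Group A versus Group B AUC beside it is optional.

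I would not replace the binary outcome by a Spearman correlation with a 0–100 pain score. The numeric scale rates overall pain, the questionnaire has several items with no single score named for this use, and 5.2 already explores change in the numeric scale.

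The cost is SAP wording and a few lines of code, with no new data, visits or patients. The downside is a wide interval with about 40 completers. It will be wider still in the subset, which would hold about 25 × 0.8 = 20 patients if dropout is equal in both groups.

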5.2 Analysis plan

The A δ :C pain threshold ratio will be recorded for each eligible and evaluable patient for both time points. We will calculate the average value of this parameter for each group (A and B) on a logarithmic scale. Then we will use a standard statistical two side t-test to compare the “A δ :C pain threshold ratio” in the painless CIPN group to the painful CIPN group. We hypothesize that the painful CIPN group will have statistically significantly higher value “A δ :C pain threshold ratio” than those without.

To assess whether the “A δ :C pain threshold ratio” predicts future painful or painless CIPN, we will conduct logistic regression analysis of the binary pain value (pain or no pain) at the time of the second testing (independent variable) on the “A δ :C pain threshold ratio” at the time of the first testing (dependent variable). It will allow us to estimate whether the “A δ :C pain threshold ratio” predicts the chances of a patient to develop pain.

As an exploratory analysis, we will explore if the “A δ :C pain threshold ratio” obtained at

the first testing session predicts an increase in the numeric pain scale at the second testing session.

5.3 Sample size

The power analysis of the preliminary data presented here was conducted by [name] (Stanford). The analysis was done on the natural logarithm scale and converted back using anti-logarithms. The geometric mean (GM) ratio of chemotherapy was 1.58 times the GM for healthy group. The GM in the diabetic group was 1.38 times the GM of the healthy group. The most variable group (Diabetics) had a standard deviation (log scale) of 0.33 and this value was used for sample size calculations.

These calculations showed that sample size of 25 subjects in each group will have 80% power to detect a 1.31 fold A δ :C pain threshold ratio in patients with painful versus painless CIPN. Based on the analysis of our preliminary data, we expect the effect size to be larger than 1.31.

It is possible that we will have more patients accrued to Group B compared to Group A because uncomfortable patients may not want to participate in as great a number. In this case, we will consider use using an “unbalanced” (“non-symmetrical”) statistical design, i.e. a design with unequal number of subjects in the two groups. If we get fewer than 25 patients with pain we will increase the number of patients in the group without pain to preserve the power of 80% in order to detect the effect size. If this approach is necessary, we will apply for a no-cost extension of the NIH SBIR.

Table 5.1 shows several possible combinations of sample sizes which will assure the power 80% to detect the effect size 1.31. The sample sizes were calculated using SAS 9.14 software, procedure proc power. The calculations are based on the use of a t-test on the natural logarithm scale with a standard deviation of 0.33, detectable effect size 0.24 on the log scale.

| Scenario | Subjects with pain | Subjects without pain |
|----------|--------------------|-----------------------|
| 1 | 25 | 25 |
| 2 | 24 | 26 |
| 3 | 23 | 27 |
| 4 | 22 | 28 |
| 5 | 21 | 29 |
| 6 | 20 | 31 |
| 7 | 19 | 34 |
| 8 | 18 | 37 |
| 9 | 17 | 42 |

Based on the new patient volume in the women’s cancer center, we expect to recruit 50 patients in 12 months. However, should the study require a non-symmetric statistical

method and its clear we will not be able to recruit 59 patients (scenario 9), we will we will request a12 month no-cost extension from the NIH/NCI.

6.0 DATA MANAGEMENT CONSIDERATIONS

6.1 Data management

The Protocol Director, or her designee, will prepare and maintain adequate and accurate participant case histories with observations and data pertinent to the study. Electronic Study-specific Case Report Forms (eCRFs) will document treatment outcomes for data analysis. Case report forms will be developed using the OnCore database system and will be maintained by the study team. eCRFs are only accessible via login to the secure OnCore system.

Data shared with LasMed, LLC will be de-identified and labeled with the alpha-numeric code assigned in OnCore. All data shared will be sent using SECURE: email. LasMed, LLC's computers are encrypted by Stanford IT.

6.2 Confidentiality

Patients will be assigned an alpha-numeric identifier in OnCore when enrolled. This database does link names and codes directly. Written inventories, such as the NPQ, will be identified with the patient's alpha-numeric code and kept in research binders, which are stored in the neuro-oncology research coordinators offices in the CCTO/Friedenreich building. Access to these offices requires an electronic Stanford ID badge.

